1. BACKGROUND AND DESIGN

Full details of the background to the study and its design are presented in the protocol.

The hypothesis that is under investigation is that patients prospectively classified to the hyper-inflammatory ARDS phenotype on the basis of clinical characteristics and a novel POC biomarker assay will have worse clinical outcomes than the hypo-inflammatory phenotype.

Aim:

The purpose of this project is to prospectively identify hyper- and hypo-inflammatory phenotypes in patients with ARDS and AHRF, and determine clinical outcomes associated with each phenotype.

Objectives:

Primary:

(i) Assess the clinical outcomes in patients with ARDS according to their prospectively defined inflammatory phenotype determined using a POC assay.

Secondary:

- (i) Assess the agreement of the phenotype allocation using a POC assay and latent class analysis (LCA) from biomarkers and the clinical study dataset
- (ii) Assess the stability of phenotype allocation over time
- (iii) Feasibility of delivering a POC assay in the NHS intensive care setting
- (iv) Identify if inflammatory phenotypes are present and influence outcomes in patients with AHRF

Patients will be eligible for the study if they meet the inclusion criteria.

Inclusion criteria

1. Patient is receiving mechanical ventilation, CPAP or high flow nasal oxygen (HFNO)
 2. a) ARDS as defined by the Berlin definition [6]
 - Onset within 1 week of identified insult
 - Within the same 24-hour time period:
 - i. Hypoxaemic respiratory failure ($\text{PaO}_2/\text{FiO}_2$ ratio $\leq 40\text{kPa}$ on $\text{PEEP} \geq 5\text{ cmH}_2\text{O}^*$)
 - ii. Bilateral infiltrates consistent with pulmonary oedema not explained by another pulmonary pathology
 - iii. Respiratory failure not fully explained by cardiac failure or fluid overload
- OR
- b) AHRF as defined by
 - Within the same 24-hour time period:
 - i. Hypoxaemic respiratory failure ($\text{PaO}_2/\text{FiO}_2$ ratio $\leq 40\text{kPa}$ on $\text{PEEP} \geq 5\text{ cmH}_2\text{O}^*$)

- ii. Unilateral infiltrates on chest imaging not fully explained by effusions, collapse, or nodules
- iii. Respiratory failure not fully explained by cardiac failure or fluid overload

The time of onset of ARDS is when the last ARDS criterion is met.

*PEEP assumed ≥ 5 cmH₂O if on HFNO

[figure not shown]
Patients will not be eligible for the study if they meet any of the exclusion criteria.

Exclusion criteria

1. Age <18 years of age

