2. More than 72 hrs after onset of ARDS/AHRF
3. Receiving ECMO at the time of recruitment
4. Treatment withdrawal imminent within 24 hours
5. DNAR (Do Not Attempt Resuscitation) order (excluding advance directives) in place*
6. Declined consent
7. Prisoners

*Intended to only exclude patients who are not receiving active medical management and are receiving palliative care.

PHIND Schematic Diagram

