7.2 Secondary Outcomes

A secondary analysis for the outcome of 60 day mortality using logistic regression to adjust for important variables (age, site, and gender) will be carried out. Odds ratio (95% CI) and p value will be reported.

Differences in 60 day mortality will also be evaluated using phenotype allocation as defined by i) commercially available assays in conjunction with a parsimonious logistic regression model and ii) LCA. For each i) and ii), analyses will be conducted by calculating: a) absolute number and percentage by phenotype, b) unadjusted percentage point difference (95%, CI), c) risk ratio (95% CI), and d) p value from Pearson's chi-square test (95% CI).

Further secondary outcomes will be analysed using both POC-derived phenotype allocation and LCA-derived phenotype allocation.

For secondary outcomes based on dichotomous variables (Re-intubation rate, 28-day mortality), absolute number and percentage by phenotype will be calculated, and p-value will be from Pearson's chi-square test.

For continuous secondary outcomes (Ventilator free days at day 28; Duration of ventilation; Length of ICU stay; Length of hospital stay), data will be reported as median (IQR) with p value derived from Mann-Whitney U test.

Analyses will be conducted to assess agreement of phenotype classification methods. Comparisons will be made between: (i) POC-derived phenotype versus phenotype from commercially available assays (defined by up to 8 different parsimonious logistic regression models [5]), (ii) POC-derived phenotype versus LCA-derived phenotype, and (iii) POC-derived phenotype versus phenotype derived from clinical classifier machine learning algorithm [11]. Cohen's kappa coefficient (95% CI) will be calculated and p-value will be from McNemar's test for agreement. All of these analyses will be performed for phenotype allocation at day 0 and at day 3. For additional comparisons between classification methods, LCA phenotype will be selected as the "gold standard" and sensitivity, specificity, negative predictive value, and positive predictive value will be calculated for all other methods. Area under the receiver operating curve (AUC) will also be calculated. These analyses will also be performed for phenotype allocation at day 0 and day 3.

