7.3 Sensitivity analysis

Primary and secondary outcomes (except those related to agreement between phenotype allocation and those related to feasibility) will be analysed and reported separately (when pertinent) for:

- AHRF cohort
- patients receiving mechanical ventilation
- patients receiving non-invasive ventilation
- patients receiving high-flow nasal oxygen
- patients receiving high-flow nasal oxygen with a flow rate of at least 30 litres per minute
- analysis excluding COVID-19 patients
- analysis restricted to patients with biosamples obtained within 24h of ARDS diagnosis
- analysis restricted to patients with biosamples obtained within 48h of ARDS diagnosis

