Duration of ventilation^b	xx.x (xx.x)	xx.x (xx.x)	xx.x (xx.x to xx.x)		x.xxx
Length of ICU stay^c	xx.x [xx.x, xx.x]	xx.x [xx.x, xx.x]			x.xxx
Length of hospital stay^c	xx.x [xx.x, xx.x]	xx.x [xx.x, xx.x]			x.xxx
28-day mortality^a					
Alive	N (xx.x%)	N (xx.x%)	xx.x (xx.x to xx.x)		
Dead	N (xx.x%)	N (xx.x%)	xx.x (xx.x to xx.x)	xx.x (xx.x to xx.x)	x.xxx

No. (%) for phenotypes and mean difference and risk ratio (95% CI) presented.

Unadjusted p-value from chi-square.

Table x.x.x Sensitivity analysis of the main clinical outcome variables, cohort restricted to patients with biosamples obtained within 24 hours of ARDS diagnosis

	Hyper-inflammatory phenotype n = (%)	Hypo-inflammatory phenotype n = (%)	Unadjusted % Point or Mean Difference (95% CI)	Unadjusted risk ratio (95% CI)	p-value	Adjusted odds ratio (95% CI)	p-value
Primary outcome ^a							
Mortality at 60 days in patients with ARDS as defined by the POC assay							
Alive	N (xx.x%)	N (xx.x%)	xx.x (xx.x to xx.x)				
Dead	N (xx.x%)	N (xx.x%)	xx.x (xx.x to xx.x)	xx.x (xx.x to xx.x)	x.xxx		
Secondary outcomes							
Adjusted 60-day mortality (phenotype defined by POC assay)						xx.x (xx.x to xx.x)	x.xxx
Time to extubation ^b	xx.x (xx.x)	xx.x (xx.x)	xx.x (xx.x to xx.x)		x.xxx		x.xxx
Intubation rate^a	N (xx.x%)	N (xx.x%)	xx.x (xx.x to xx.x)		x.xxx		x.xxx
Re-intubation rate ^a	N (xx.x%)	N (xx.x%)	xx.x (xx.x to xx.x)		x.xxx		x.xxx
Ventilator free days at day 28 ^b	xx.x (xx.x)	xx.x (xx.x)	xx.x (xx.x to xx.x)		x.xxx		x.xxx
Duration of ventilation ^b	xx.x (xx.x)	xx.x (xx.x)	xx.x (xx.x to xx.x)		x.xxx		x.xxx
Length of ICU stay ^c	xx.x [xx.x, xx.x]	xx.x [xx.x, xx.x]			x.xxx		
Length of hospital stay ^c	xx.x [xx.x, xx.x]	xx.x [xx.x, xx.x]			x.xxx		
28-day mortality ^a							
Alive	N (xx.x%)	N (xx.x%)	xx.x (xx.x to xx.x)				
Dead	N (xx.x%)	N (xx.x%)	xx.x (xx.x to xx.x)	xx.x (xx.x to xx.x)	x.xxx	xx.x (xx.x to xx.x)	x.xxx

^a No. (%) for phenotypes and mean difference and risk ratio (95% CI) presented and unadjusted p-value from chi-square and adjusted p-value from logistic regression adjusted for age, gender, and site.

^b Mean(SD) for phenotypes and mean difference (95% CI) presented, unadjusted.

^c Median[IQR] and p-value from Mann-Whitney test.

Table x.x.x Secondary analyses, cohort restricted to patients with biosamples obtained within 24 hours of ARDS diagnosis

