	Hyper-inflammatory phenotype n = (%)	Hypo-inflammatory phenotype n = (%)	Unadjusted % Point or Mean Difference (95% CI)	Unadjusted Risk ratio (95% CI)	p-value
Mortality at 60 days in patients with ARDS defined by commercially-available assays and parsimonious model					
Alive	N (xx.x%)	N (xx.x%)	xx.x (xx.x to xx.x)		
Dead	N (xx.x%)	N (xx.x%)	xx.x (xx.x to xx.x)	xx.x (xx.x to xx.x)	x.xxx
Mortality at 60 days in patients with ARDS defined by the complete data-set using latent class analysis					
Alive	N (xx.x%)	N (xx.x%)	xx.x (xx.x to xx.x)		
Dead	N (xx.x%)	N (xx.x%)	xx.x (xx.x to xx.x)	xx.x (xx.x to xx.x)	x.xxx
Secondary outcomes using phenotype allocation defined by the complete dataset using latent class analysis					
Time to extubation^b	xx.x (xx.x)	xx.x (xx.x)	xx.x (xx.x to xx.x)		x.xxx
Intubation rate^a	N (xx.x%)	N (xx.x%)	xx.x (xx.x to xx.x)		x.xxx
Re-intubation rate^a	N (xx.x%)	N (xx.x%)	xx.x (xx.x to xx.x)		x.xxx
Ventilator free days at day 28^b	xx.x (xx.x)	xx.x (xx.x)	xx.x (xx.x to xx.x)		x.xxx
Duration of ventilation^b	xx.x (xx.x)	xx.x (xx.x)	xx.x (xx.x to xx.x)		x.xxx
Length of ICU stay^c	xx.x [xx.x, xx.x]	xx.x [xx.x, xx.x]			x.xxx
Length of hospital stay^c	xx.x [xx.x, xx.x]	xx.x [xx.x, xx.x]			x.xxx
28-day mortality^a					
Alive	N (xx.x%)	N (xx.x%)	xx.x (xx.x to xx.x)		
Dead	N (xx.x%)	N (xx.x%)	xx.x (xx.x to xx.x)	xx.x (xx.x to xx.x)	x.xxx

No. (%) for phenotypes and mean difference and risk ratio (95% CI) presented.

Unadjusted p-value from chi-square.

Table x.x.x Sensitivity analysis of the main clinical outcome variables, cohort restricted to patients with biosamples obtained within 48 hours of ARDS diagnosis

	Hyper-inflammatory phenotype n = (%)	Hypo-inflammatory phenotype n = (%)	Unadjusted % Point or Mean Difference (95% CI)	Unadjusted risk ratio (95% CI)	p-value	Adjusted odds ratio (95% CI)	p-value
Primary outcome ^a							
Mortality at 60 days in patients with ARDS as defined by the POC assay							
Alive	N (xx.x%)	N (xx.x%)	xx.x (xx.x to xx.x)				
Dead	N (xx.x%)	N (xx.x%)	xx.x (xx.x to xx.x)	xx.x (xx.x to xx.x)	x.xxx		
Secondary outcomes							
Adjusted 60-day mortality (phenotype defined by POC assay)						xx.x (xx.x to xx.x)	x.xxx
Time to extubation ^b	xx.x (xx.x)	xx.x (xx.x)	xx.x (xx.x to xx.x)		x.xxx		x.xxx
Intubation rate^a	N (xx.x%)	N (xx.x%)	xx.x (xx.x to xx.x)		x.xxx		x.xxx
Re-intubation rate ^a	N (xx.x%)	N (xx.x%)	xx.x (xx.x to xx.x)		x.xxx		x.xxx

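### Time from ARDS onset to sampling enters no model and is examined only through the nested 24 h and 48 h restricted cohorts; a covariate and a phenotype-by-time fit in all ARDS patients should be added beside them

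*Supplement*

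**What the plan says.** Section 1 of the SAP excludes patients who are "More than 72 hrs after onset of ARDS/AHRF" and fixes the start of that clock: "The time of onset of ARDS is when the last ARDS criterion is met".

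Sampling time then appears in one role. Section 7.3 lists an "analysis restricted to patients with biosamples obtained within 24h of ARDS diagnosis" and an "analysis restricted to patients with biosamples obtained within 48h of ARDS diagnosis". Section 8.5 repeats both, and Appendix 1 provides a pair of tables for each, the first pair being for the "cohort restricted to patients with biosamples obtained within 24 hours of ARDS diagnosis".

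The models are specified without it:
- Section 7.1: the primary 60-day mortality comparison is an unadjusted chi-square test in the ARDS patients.
- Section 7.2: adjusted 60-day mortality uses age, site and gender. Section 8.5 names age and gender only. Footnote a in Appendix 1, including under the 24 h table, gives "adjusted p-value from logistic regression adjusted for age, gender, and site".
- Section 8.5: the adjusted secondary outcomes use age, comorbid disease, cause of ARDS, vasopressor need and oxygenation ratio.

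Time from onset to sample is also absent from the baseline characteristics listed in section 8.3.

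**The concern.** A patient sampled late has already survived longer than one sampled early. If the biomarkers move over the first days, that patient may also be labelled differently. Sampling time could then be related to both phenotype and death, and the full-cohort adjusted odds ratio would carry some of that confounding.

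The two restricted analyses show that the sponsor regards timing as worth checking, but they check it by discarding patients. The 24 h cohort lies inside the 48 h cohort, so the two are not independent checks, and the 48 h cohort still mixes earlier and later samples. The 24 h table reports a p-value. An association that had not changed could lose significance there simply because the cohort is smaller, and be taken for dependence on timing.

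The restricted cohorts also count from diagnosis, whereas the time point that the SAP defines is onset.

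**Working it through.** **1. The plan's own figure.** Inputs from section 5: mortality 17% and 32%, group sizes 347 and 116, two-sided alpha 0.05, stated power 90%.

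- Pooled proportion: (347 × 0.17 + 116 × 0.32)/463 = 0.2076.
- Null SE: √[0.2076 × 0.7924 × (1/347 + 1/116)] = 0.0435.
- Alternative SE: √[0.17 × 0.83/347 + 0.32 × 0.68/116] = 0.0478.
- Power: Φ[(0.15 − 1.96 × 0.0435)/0.0478] = Φ(1.355) = 91.2%. The stated 90% is reproduced.

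**2. Cost of restriction.** The full-cohort half-width is 1.96 × 0.0478 = 9.4 points. Keeping a share s of both groups multiplies each SE by 1/√s. The SAP does not give s, so a range is assumed:

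| Share kept | Half-width (points) | Power |
|---|---|---|
| 100% | 9.4 | 91% |
| 80% | 10.5 | 85% |
| 2/3 | 11.5 | 78% |
| 1/2 | 13.2 | 67% |
| 1/3 | 16.2 | 51% |

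**3. Cost of adjustment.** This was simulated in cohorts of 463, 1,500 runs per setting, with a true log odds ratio of 0.83 (the logit of 32% minus the logit of 17%). Assumptions: sampling lies within 0–72 h; per 24 h, the log odds of being hyper-inflammatory fall by 0.2 and the log odds of death rise by 0.2. Entries are the median SE of the phenotype log odds ratio:

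| Share sampled by 24 h / 48 h | Full, unadjusted | Full + time | Full + time + interaction, read at 12 h | 48 h cohort | 24 h cohort |
|---|---|---|---|---|---|
| 33% / 67% (uniform) | 0.247 | 0.250 | 0.385 | 0.305 | 0.439 |
| 44% / 83% | 0.247 | 0.249 | 0.347 | 0.272 | 0.377 |
| 70% / 96% | 0.248 | 0.250 | 0.274 | 0.253 | 0.299 |

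The time covariate raises the SE by about 1% (0.250/0.247). The interaction fit is only somewhat more precise than the 24 h cohort: 0.385 against 0.439 with uniform times. If most samples are early, the 48 h cohort loses almost nothing.

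**4. Possible size of the confounding.** Suppose three equal 24 h bands have hyper-inflammatory shares of 35%, 25% and 15%, baseline risks of 26%, 21% and 16%, and no phenotype effect. The spurious risk difference is cov(share, risk)/[p(1 − p)].

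- Full cohort: (0.10 × 0.05 × 2/3)/(0.25 × 0.75) = 1.8 points.
- 48 h cohort: (0.05 × 0.025)/(0.30 × 0.70) = 0.6 points.
- 24 h cohort: 0, by construction, because nothing varies within a band.

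If the same change is linear over 72 h, the full-cohort figure is (0.20 × 0.10/12)/(0.25 × 0.75) = 0.9 points. These risks average 21%, above the 17% in section 5.

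**5. If the association itself changes with time.** Assumptions: uniform sampling, 17% v 32% for samples before 24 h, log odds ratio fading to 0 by 72 h, 1,000 runs. Median log odds ratios: full unadjusted 0.57, full with time covariate 0.57, 48 h cohort 0.74, 24 h cohort 0.85. A separate simulation with a fading effect gave 0.56 for the adjusted full cohort and 0.81 for the 24 h cohort. The main-effect covariate does not register the change; restriction does.

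**The case against.** The strongest reply is that restriction and adjustment answer different questions. The 24 h and 48 h analyses ask whether the association holds when the sample is early. A main-effect covariate assumes one common association and cannot answer that. Step 5 bears this out and it stands. A reader might infer that one covariate could replace the restricted analyses or become the main check on timing; the documents and the calculations do not support that. A phenotype-by-time term does address the restriction's question, but with only part of the precision gain.

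Four further points stand:
- The primary analysis and the existing adjusted mortality model keep every ARDS patient. The loss falls on analyses labelled as sensitivity analyses, for which the SAP sets no significance rule. The tables already report risk differences, risk ratios and adjusted odds ratios with 95% CIs.
- The 72 h limit governs recruitment. A sampling range of 0–72 h is inferred; section 3.1 leaves the timing of data collection to the protocol, which is not shown.
- In the banded scenario of step 4, the planned 48 h analysis already cuts the confounding from 1.8 to 0.6 points, against a design difference of 15 points.
- A reader might infer from secondary objective (ii) that the plan doubts phenotype stability. It only names stability as something to assess, and covers day 0 to day 3 by kappa, McNemar's test and latent transition analysis.

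The reply does not show a reason to leave the time out of the adjusted model. The restricted cohorts already need a start time and a sample time, and the term costs almost no precision. The diagnosis/onset difference is one of wording with no demonstrated effect on results, but it leaves the cohort boundary on an undefined time point.

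**Conclusion.** The point holds as a low-cost improvement and does not show an error in the primary analysis. Onset-to-sample time is in no listed model, and the only planned check on it gives up precision. If two thirds to one third of patients are kept, the half-width grows from 9.4 to between 11.5 and 16.2 points, and power for the design difference falls from 91% to between 78% and 51%. These figures rest on section 5's rates and group sizes, on equal retention in both phenotypes, and on an assumed share kept. With 70% sampled by 24 h and 96% by 48 h, the simulated SEs are 0.299 and 0.253 against 0.250 for the adjusted full cohort, so the loss is then modest at 24 h and negligible at 48 h.

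The confounding that might be removed looks small: about 1 to 2 points under the assumed gradients. The case for the change is that it uses every ARDS patient, draws on times the plan already needs, and complements the restricted analyses.

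**What to change.** 1. In sections 7.2 and 8.5, and in footnote a of Appendix 1, add hours from ARDS onset (as defined in section 1) to the baseline sample as a continuous covariate in the secondary adjusted 60-day mortality model, fitted to all ARDS patients. Use the same covariate list in all three places, since section 8.5 currently omits site.
2. Report a second fit that adds a phenotype-by-time term, with its 95% CI and the phenotype odds ratio at a stated time such as 12 h.
3. Keep the 24 h and 48 h analyses with their present standing. State that they are read by estimate and 95% CI, and that loss of significance alone is not evidence of dependence on timing.
4. Measure the 24 h and 48 h limits from the defined onset, in sections 7.3 and 8.5 and in the Appendix 1 table titles.
5. Add onset-to-sample time, by phenotype and in total, to the baseline list in section 8.3, so that readers can see how many patients each restriction removes.

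The cost is SAP wording, one model term and one extra fit. No new data should be needed, provided the start time held for the restricted cohorts is, or can be set to, the defined onset. The primary analysis is unchanged.
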